7.2.5 Physical Examination, Vital Signs and ECG

A physical examination and vital signs (systolic and diastolic blood pressure, pulse rate, respiratory rate, and temperature) will be conducted during the Screening period and on each study visit (Days 1, 8, 15, 22, and 28) of every cycle of CE. A 12-lead ECG (rhythm, heart rate, and PR, QRS, and QTc intervals) will be performed during the Screening period, on Cycle 1 Day 8, Cycle 1 Day 28, and as clinically indicated.

8. ADVERSE EVENTS

8.1 Definitions

8.1.1 Adverse Event

The term “adverse event” includes any sign, symptom, syndrome, or illness that appears or worsens in a subject during the period of observation in the clinical study and that may impair the wellbeing of the subject. The term also covers laboratory findings or results of other diagnostic procedures that are considered to be clinically significant (*e.g.*, that require unscheduled diagnostic procedures or treatment measures, or result in withdrawal from the study).

The adverse event may be:

- A new illness/condition;
- Worsening of a sign or symptom of the condition under treatment, or of a concomitant illness/condition;
- An effect of the study drug; or
- A combination of 2 or more of these factors.

No causal relationship with the study drug or with the clinical study itself is implied by the use of the term “adverse event.”

Surgical procedures themselves are not adverse events; they are therapeutic measures for conditions that require surgery. The condition(s) for which the surgery is required may be an adverse event. Planned surgical measures permitted by the clinical study protocol and the condition(s) leading to these measures are not adverse events.

When a clear diagnosis is available that explains the abnormal objective findings, this diagnosis will be recorded as an adverse event and not the abnormal objective findings (*e.g.*, viral hepatitis will be recorded as the adverse event and not the transaminase elevation). If a definitive diagnosis is not available, then the sign(s) (*e.g.*, clinically significant elevation of transaminase levels) or symptom(s) (*e.g.*, abdominal pain) will be recorded as the adverse event.

Adverse events fall into the categories “serious” and “non-serious.”

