2.2 Secondary

In subjects with resistant AML, to

- Determine the safety and feasibility of treatment with ciprofloxacin and etoposide;
- Measure the response duration, progression-free and overall survival (PFS and OS respectively);
- Estimate the incidence of Grade ≥ 3 adverse events following treatment with ciprofloxacin and etoposide at the MTD.

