4.4.1 Non- Hematologic Toxicity

For any Grade 3 or greater non-hematologic adverse event (AE), deemed related or possibly related to the study intervention and/or the discretion of the investigator, the subject to stop the study drugs.

Management of non-hematologic toxicities such as nausea, vomiting, mucositis, enteritis, and/or diarrhea will follow institutional guidelines.

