7.2.4 Clinical laboratory assessments

Clinical laboratory assessments are outlined in [Table 1](#).

Hematology assessments will be performed during the Screening period and on Days 1, 8, 15, 22, and 28 of each cycle. The hematology assessments will include:

- Complete blood count (CBC) including hemoglobin, hematocrit, white blood cell (WBC) absolute differential including circulating blasts, and platelet count.

Blood chemistry assessments will be performed during the Screening period on Days 1, 8, 15, 22, and 28 of each cycle. The chemistry assessments will include:

- Electrolytes: (sodium, potassium, calcium, magnesium, phosphorous, bicarbonate, and chloride);
- Renal function: (BUN, creatinine, and uric acid);
- Liver function: SGOT (also known as AST), SGPT (also known as ALT), total bilirubin;
- LDH, and alkaline phosphatase; and
- Other: (glucose, albumin, and total protein).

Serum pregnancy tests for females of childbearing potential will be performed during the screening period and on day 28 of each cycle. If delayed, a pregnancy test will be repeated within 7 days of the first day of the next cycle.

Approximately 50 mL of blood will be collected for safety assessments from each subject over the course of each 28-day cycle.

Abnormal, clinically significant results as assessed by the Principal Investigator should be repeated to rule out laboratory error. Persistent relevant abnormal changes from baseline must be followed up until the cause is determined or until they return to the premedication value. Hematology and serum chemistry will be carried out according to the standard operating procedures by the validated local laboratory.

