11.3 Analysis Methods

11.3.1 Safety

Safety evaluation will include monitoring for adverse events, scheduled laboratory assessments, vital sign measurements, ECGs, and physical examinations. The intensity of adverse changes in physical signs or symptoms will be graded according to the CTCAE version 4. For all other adverse events not listed in the CTCAE, the intensity of events will be assessed by the PI using a 5-point scale as described in [Section 8.3.2](#).

The number of adverse events and the incidence of adverse events will be summarized. Adverse events will be summarized by maximum intensity (as described in [Section 8.3.2](#)) and relationship to study drug for each treatment group. Separate summaries will be provided for all adverse events, serious adverse events, treatment-related adverse events, and other significant adverse events (*e.g.*, adverse events leading to study discontinuation).

Clinical laboratory results will be listed by subject or, as appropriate, summarized descriptively by treatment group, which will include a display of change from baseline. Laboratory values outside of the normal ranges will be identified. Clinically significant hematologic laboratory abnormalities (*i.e.*, meet Grade 3, 4, or 5 criteria according to CTCAE) will be listed and summarized.

Physical examination, vital sign, and ECG data will be listed for each subject at each visit. If appropriate, descriptive statistics for vital signs, both observed values and changes from baseline, will be summarized by treatment group.

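### Section 11.3.1 plans a CTCAE-graded summary for hematologic laboratory abnormalities only, so a Grade 3 or higher chemistry value judged not clinically significant may go uncounted by grade

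*Combined protocol and SAP*

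**What the plan says.** Section 2.2 lists as a secondary objective an estimate of the incidence of Grade 3 or higher "adverse events following treatment with ciprofloxacin and etoposide at the MTD".

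Section 8.1.1 decides when a laboratory result becomes an adverse event: "The term also covers laboratory findings or results of other diagnostic procedures that are considered to be clinically significant". The examples, introduced by an e.g., are results "that require unscheduled diagnostic procedures or treatment measures, or result in withdrawal from the study". No grade threshold is given. The same section names "clinically significant elevation of transaminase levels" as something to record when there is no definitive diagnosis. Section 7.2.4 says who judges: "Abnormal, clinically significant results as assessed by the Principal Investigator should be repeated to rule out laboratory error".

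Section 11.3.1 sets out the laboratory reporting. For all tests: "Clinical laboratory results will be listed by subject or, as appropriate, summarized descriptively by treatment group, which will include a display of change from baseline". Values outside the normal range are to be identified. The listing and summary by CTCAE Grade 3, 4 or 5 is confined to "Clinically significant hematologic laboratory abnormalities".

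Section 4.4.2 assumes that cytopenia present at diagnosis is due to the leukemia. Section 4.4.1 depends on grade for the other organ systems: "For any Grade 3 or greater non-hematologic adverse event (AE), deemed related or possibly related to the study intervention".

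**The concern.** The term *clinically significant* has two meanings. In Sections 8.1.1 and 7.2.4 it is a judgment, illustrated by consequences. In Section 11.3.1 it means Grade 3 to 5, but only for hematology. Chemistry has only the judgment.

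The graded laboratory table therefore covers the results that are hardest to attribute to the drugs, since low counts may come from the disease. Liver, kidney and electrolyte values, which are easier to read as drug effects, have no graded table. If some high-grade chemistry values are judged not clinically significant, the Grade 3 or higher incidence omits them and no graded output sits beside it to show how many there were.

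**Working it through.** The plan states no figure that can be reproduced here, so the check is mainly of the text.

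**Step 1. Where a post-dose Grade 3 or higher value goes**

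| Value | Judged clinically significant | In Grade ≥ 3 adverse event incidence | In a CTCAE-graded laboratory summary | In ungraded listing or summary, with range flag |
|---|---|---|---|---|
| Hematology | yes | yes | yes | yes |
| Hematology | no | no | yes | yes |
| Chemistry | yes | yes | no | yes |
| Chemistry | no | **no** | **no** | yes |

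The hematology rows read Section 11.3.1 as defining significance by grade, which is what its parenthesis says. Only the last row has no graded output.

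**Step 2. Whether another route supplies a grade**

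- *Dose-limiting toxicity.* Section 3.3.2 works by grade of toxicity, with no test of clinical significance, and Section 11.2.2 tabulates the events. It covers only Phase Ib Cycle 1 and only events the principal investigator considers related. The synopsis sets the non-hematologic threshold at Grade 3 or higher and Section 3.3.2 at above Grade 3. The two must be reconciled, because this decides whether a Grade 3 chemistry value is caught here.
- *Toxicity assessment at visits.* The synopsis and Table 1 schedule CTCAE assessment, but Section 11.3.1 plans no table from it other than the adverse event summaries.
- *Out-of-range flags.* The inclusion criteria admit AST and ALT up to 2.5 times the upper limit of normal, so a subject can be flagged at entry. A flag does not separate that from a new high-grade value.
- *Change from baseline.* A descriptive summary of change gives no count of subjects by grade.

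**Step 3. Whether the data exist**

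Section 7.2.4 schedules chemistry at screening and on Days 1, 8, 15, 22 and 28 of each cycle. Grades can be derived without a new procedure.

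**Step 4. Possible size, on an assumption**

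Let q be the share of subjects with a Grade 3 or higher chemistry value judged not clinically significant. The documents do not give q. With n = 24, the evaluable target in Section 11.1:

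- expected subjects = 24 × q
- chance of at least one = 1 − (1 − q)^24
- largest shift in incidence = q, if none of these subjects has another recorded Grade 3 or higher event
- shift if a share s already has such an event, independently = q × (1 − s)

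For s, Section 1.2 reports Grade 3/4 neutropenia in about two thirds of patients on a different oral etoposide schedule. Taking s = 2/3:

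| q (assumed) | Subjects of 24 | Chance of at least one | Largest shift (points) | Shift if s = 2/3 (points) |
|---|---|---|---|---|
| 0% | 0 | 0 | 0 | 0 |
| 5% | 1.2 | 0.71 | 5 | 1.7 |
| 10% | 2.4 | 0.92 | 10 | 3.3 |
| 20% | 4.8 | 0.995 | 20 | 6.7 |

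For scale, the standard error of an incidence of 2/3 at n = 24 is √(0.667 × 0.333 / 24) = 0.096, or 9.6 points. The safety population in Section 11.2.1 is not the evaluable population. With the 30 subjects that Section 11.1 plans to enrol, the expected counts are 0, 1.5, 3.0 and 6.0.

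**The case against.** Three stronger readings are tempting, and the documents support none of them.

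*Such values are counted in no planned table.* Section 11.3.1 lists or summarises all laboratory results with change from baseline and flags out-of-range values, so a large elevation could be seen there. A related one in Phase Ib Cycle 1 can be a tabulated dose-limiting toxicity, and Section 10 has the safety committee receive a summary of toxicities. What is missing is a count by grade.

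*The Grade 3 or higher incidence is understated.* That happens only if high-grade values are judged not significant. Several passages point the other way: the examples in Section 8.1.1 are not exhaustive, a transaminase rise without a diagnosis is recordable, Section 7.2.4 calls for repeat testing and follow-up, and Section 11.3.1 itself equates significance with Grade 3 to 5 for hematology. Under-counting is possible but not shown.

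*The rule is circular, because a value becomes an adverse event only once someone has acted on it.* Under Section 7.2.4 the principal investigator's assessment comes first and the repeat test follows. Action is an example of significance, not a condition for it.

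A reader might also want Section 8.1.1 changed so that Grade 3 or higher chemistry values are adverse events by definition. Requiring clinical significance is a defensible choice, and the change has consequences. Chemistry would be coded by grade while hematology stayed on judgment. New events could engage Section 4.4.1. They would also feed the Phase II safety rule in Section 9.3, which counts subjects with adverse events (5 of 14) and states no grade. As an illustration, if the share of subjects counted under that rule rose from 35% to 40%, the binomial chance of 5 or more in 14 would rise from 0.58 to 0.72.

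What remains is that the graded summary is restricted to hematology and nothing in the plan requires that restriction.

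**Conclusion.** The point holds as a gap in reporting. A Grade 3 or higher chemistry value judged not clinically significant would be in neither the secondary-objective incidence nor any CTCAE-graded laboratory summary, the Phase Ib Cycle 1 dose-limiting toxicity route apart. High-grade hepatic, renal or electrolyte toxicity may be under-counted by an unknown amount, possibly zero. The figures in the working rest on an assumed q and, in the last column, on independence and a two-thirds rate borrowed from another schedule; they show scale only. The primary endpoint and the Simon two-stage design are unaffected. The change is worth making because it is nearly free.

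**What to change.** In Section 11.3.1, delete the word *hematologic* from the sentence on Grade 3 to 5 abnormalities. Add that every CTCAE-gradable hematology and chemistry parameter will be tabulated by worst post-dose grade and as a shift from baseline grade, in the safety population, and shown beside the Grade 3 or higher adverse event incidence. A reader can then see how many high-grade laboratory values were not recorded as adverse events.

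Leave the definition in Section 8.1.1 unchanged. Whether a Grade 3 or higher laboratory value is an adverse event by definition, and how that would relate to Section 4.4.1 and to the stopping rule in Section 9.3, is for the sponsor to reconcile.

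The cost is slightly more table programming. No sample, visit or procedure is added.

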8.1.2 Serious Adverse Event

A serious adverse event is one that at any dose of the study drug or at any time during the period of observation:

- Results in death;
- Is life-threatening;
- Requires inpatient hospitalization or prolongation of existing hospitalization;
- Results in persistent or significant disability/incapacity;
- Is a congenital anomaly/birth defect; or
- Is medically important.

Life-threatening means the subject was at immediate risk of death at the time of the serious adverse event; it does not refer to a serious adverse event that hypothetically might have caused death if it were more severe.

Persistent or significant disability or incapacity means there is a substantial disruption of a person’s ability to carry out normal life functions.

Medical and scientific judgment should be exercised in deciding whether other adverse events may be considered serious because they jeopardize the subject or may require intervention to prevent one of the other outcomes listed in the definition above. Examples of such events are: intensive treatment in an emergency room or at home for allergic bronchospasm, blood dyscrasias, or convulsions that do not result in hospitalization; or development of drug dependency or drug abuse. “Medically important” should be marked only if no other serious criteria are met.

An “unexpected SAE” is any SAE for which the nature, specificity or severity is not consistent with the currently known adverse reaction to ciprofloxacin or etoposide

Clarification of the difference in meaning between “severe” and “serious”

The term “severe” is often used to describe the intensity (severity) of a specific event (as in mild, moderate, or severe myocardial infarction); the event itself, however, may be of relatively minor medical significance (such as severe headache). Any grade ≥ 3 adverse event per CTCAE is generally considered severe AE. This is not the same as “serious,” which is based on the outcome or action criteria usually associated with events that pose a threat to life or functioning. Seriousness (not severity) serves as a guide for defining regulatory reporting obligations.

8.1.3 Non-Serious Adverse Event

A non-serious adverse event is any adverse event not meeting any of the serious adverse event criteria.

8.2 Period of Observation

For the purpose of this study, the period of observation for adverse events starts on the day the subject signs informed consent. For subjects who fail screening, the period of observation ends on the date of screening failure. Treated subjects, including those who were prematurely discontinued from the study, will be followed for any adverse events that occur during the study from the time the subject signs the informed consent form until 28 days (± 7 days) following the last dose of study treatment (i.e., the Follow-up Visit). However, if another course of anti-cancer therapy is initiated prior to the 28-day follow-up period visit, collection of adverse events will no longer be performed, with the exception of events that may be possibly, probably, or definitely related to the investigational agent or are clinically significant.

8.3 Documenting and Reporting of Adverse Events by Investigator

All adverse events that occur after the subject has signed informed consent must be documented on the pages provided in the case report form. The following approach will be taken for documentation:

- All adverse events (whether serious or non-serious) must be documented on the “Adverse Event” page of the case report form.
- For adverse events classified as serious (see [Section 8.4.1](#)) the Investigator must report the event within 24 hours to UFHCC PMO. All SAE's must also be reported to the IRB and DISC in accordance with the institution's policy.

Every attempt should be made to describe the adverse event in terms of a diagnosis that encompasses the component signs and symptoms. If only nonspecific signs or symptoms are present, then these should be recorded as separate diagnoses on the pages of the case report form.

All subjects who have adverse events, whether considered associated with the use of study drug or not, must be monitored to determine the outcome. The clinical course of the adverse event will be followed according to accepted standards of medical practice, even after the end of the period of observation, until a satisfactory explanation is found or the Principal Investigator considers it medically justifiable to terminate follow-up. Should the adverse event result in death, a full pathologist’s report should be supplied, if possible.

8.3.1 Assessment of Causal Relationship of Study Drug

The Investigator will provide an assessment of the potential causal relationship between adverse

events and study medication by determining whether or not there is a reasonable possibility that the event was caused by the study medication. The relationship or association of the adverse event to the study medication will be characterized as not related, probably not related, possibly related, probably related, or related:

Not Related: There is not a temporal relationship to the study drug administration or the adverse event is clearly due only to the progression of the underlying disease state, intercurrent illness, concomitant medication, concurrent therapy or other known cause.

Probably Not Related: There is little or no chance that the study drug administration caused the adverse event; the event is most likely due to another competing cause, including intercurrent illness, progression or expression of the disease state, or a reaction to a concomitant medication or concurrent therapy appearing to explain the reported adverse event.

Possibly Related: The association of the adverse event with the study drug administration is unknown; however, the adverse event is not reasonably attributed to any other condition.

Probably Related: When a reasonable temporal relationship exists between the adverse event and the study drug administration; significant symptoms abate upon discontinuation of the study drug and there is a reasonable explanation based on known characteristics of the study drug and there is no clear association with preexisting disease or therapy, intercurrent illness, concurrent therapy or other factor(s).

Related: When the adverse event is a known side effect of the study drug or there is a temporal relationship to the administration of the study drug; or the adverse event reappears upon re-administration of the study drug (rechallenge); or the significant symptoms of the adverse event abate upon discontinuation of the study drug (dechallenge).

8.3.2 Intensity of Adverse Events

The intensity of adverse changes in physical signs or symptoms will be graded according to the CTCAE version 4. For all other adverse events not described in the CTCAE, the intensity will be assessed by the Investigator using the following categories:

Mild (Grade 1) – transient or mild discomfort; no limitation in activity; no medical intervention/therapy required.

Moderate (Grade 2) – mild to moderate limitation in activity, some assistance may be needed; no or minimal medical intervention/therapy required.

Severe (Grade 3) – marked limitation in activity, some assistance usually required; medical intervention/therapy required, hospitalization is possible.

Life-threatening (Grade 4) – extreme limitation in activity, significant assistance required; significant medical intervention/therapy required, hospitalization or hospice care probable.

Death (Grade 5) – the event resulted in death.

8.3.3 Action Taken with Study Drug

The action the Investigator took with study drug as a result of the event should be recorded as one of the following:

None – No action was taken with regard to the study drug as a result of the adverse event.

Interrupted – Study drug was stopped due to the adverse event, but was later resumed at the

same dose.

Dose decreased – The dose of study drug was decreased as a result of the adverse event.

Permanently discontinued – The subject was withdrawn from the study due to the adverse event.

Only one item should be chosen. If multiple actions apply, the following “worst case” scenario hierarchy should be used to determine the preferred entry:

Discontinued > dose decreased > therapy interrupted.

8.3.4 Definition of Outcome

The outcome of the AE should be recorded as one of the following:

Resolved without sequelae – The subject fully recovered from the adverse event with no observable residual effects.

Resolved with sequelae – The subject recovered from the adverse event with observable residual effects.

Not resolved – The adverse event was present at the time of last observation.

Death – The subject died as a result of the adverse event.

